14.3. EXPLORATORY EFFICACY

14.3.1. EXPLORATORY EFFICACY VARIABLES & DERIVATIONS

14.3.1.1. Analysis of the primary and secondary endpoint components at Week 2, 6, 10 and 12

Subject's Global Assessment of Disease Status

Descriptive statistics of the subject's global assessment of disease status (as collected in the eCRF) for each time point (including baseline) and the change from baseline will be presented.

Document:	x:\biostatistics\documentation\sap\pya18238_izana_ izn-101	_sap_v1_0_2019050.docx	
Author:		Version Number:	1.0
		Version Date:	07May2019
Template No.:	CS_TP_BS016 Revision 5	Reference: CS_W	_BS00

Effective Date: 01Apr2018

Subject's Assessment of Spinal Pain,

Descriptive statistics of the subject's assessment of spinal pain (as collected in the eCRF) for each time point (including baseline) and the change from baseline will be presented.

Function (BASFI)

Descriptive statistics of each BASFI item (as collected in the eCRF) and the overall BASFI score (as derived in the eCRF) for each time point (including baseline) and the change from baseline will be presented.

Bath ankylosing spondylitis disease activity index (BASDAI)

Descriptive statistics of each BASDAI item (as collected in the eCRF), and the BASDAI score (as derived in the eCRF) for each time point (including baseline) and the change from baseline will be presented.

14.3.1.2. Proportion of subjects who show a radiological response on MRI at 12 weeks

The radiological response is collected in an external data transfer and will be summarized descriptively in the Clinical Study Report.

14.3.1.3. Proportion of subjects who achieve ASAS20 clinical response at Weeks 2 and 10

The ASAS20 will be derived as defined for the primary endpoint in Section 14.1.1.

14.3.1.4. Proportion of subjects who achieve ASDAS-CRP response at Weeks 2 and 10

The ASDAS-CRP response will be derived as defined in the secondary endpoint Section 14.2.1.3.

14.3.1.5. Joint count, tendon swelling, and enthesitis at Weeks 2, 6, 10, and 12

The change from baseline to the time point of interest for the following variables, derived in the eCRF, will be summarized:

- Total number of swollen joints
- Total number of tender/painful joints
- Leeds Enthesis Scores

 Document:
 x:\biostatistics\documentation\sap\pya18238_izana_izn-101_sap_v1_0_2019050.docx

 Author:
 Version Number:
 1.0

 Version Date:
 07May2019

Template No.: CS_TP_BS016 Revision 5

Effective Date: 01Apr2018

Copyright © 2009, 2010, 2012, 2016, 2018 IQVIA. All rights reserved. The contents of this document are confidential and proprietary to IQVIA Holdings Inc. and its subsidiaries. Unauthorized use, disclosure or reproduction is strictly prohibited.

Reference: CS WI BS00

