The study will consist of a maximum 4-week Screening Period, followed by a 12-week double-blind treatment evaluation period, followed by a 16-week safety follow-up period, for a maximum study duration of approximately 32 weeks or 224 days per subject. Eligible subjects will be randomised on Day 1 of Week 0 and receive study treatment administered sc on Day 1 of Week 0, Week 2 (loading dose), Week 6 and Week 10. Subjects will return on Week 12 for an End of Treatment (EoT) visit during which efficacy and safety assessments will be performed. Subjects will have a follow-up visit 16 weeks after the EoT visit.

Number of Investigators and Study Centres:

Up to 10 Investigators and 10 study centres are expected to participate in this study.

Number of Subjects:

Approximately 70 subjects will be screened to achieve 42 subjects randomly assigned to study treatment (36 on active treatment and 6 on placebo) and 42 evaluable subjects for an estimated total of 36 evaluable subjects on the active treatment arm and 6 evaluable subjects in the placebo treatment arm.

Treatment Groups and Duration:

Test product, dose and mode of administration:

Namilumab 150 mg sc administered at Weeks 0, 2, 6 and 10.

Reference therapy, dose and mode of administration:

Matching placebo solution sc administered at Weeks 0, 2, 6 and 10.

Statistical Methods:

The primary endpoint will be ASAS20. Based on literature data, the prior for the placebo and namilumab groups will follow a beta distribution with mean of 0.3 and 0.6, respectively. Weighting for the priors will be equivalent to 20 and 5 subjects, respectively. Sample size is the smallest sample size so that P{ θ act > θ pbo| Y(HA)} >0.927 with probability 0.9, assuming true response rates of 0.3 and 0.6 for the control and namilumab arms, respectively. For a 6:1 randomisation, 42 patients need to be randomised.

Efficacy endpoints will be summarised by treatment group and visit. The posterior distribution of the primary endpoint will be computed using the conjugate priors, and the mean, standard deviation, and 5th, 10th, 25th, 50th, 75th, 90th, and 95th percentiles of the posterior distribution will be presented.

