3.0 OBJECTIVES AND ENDPOINTS

Table 4Study Objectives and Endpoints

Objectives	Endpoints			
Primary				
• To assess the efficacy of namilumab 150 mg subcutaneous (sc), given on Weeks 0, 2, 6 and 10 in subjects with axSpA	• Proportion of subjects who achieve an ASAS20 clinical response at Week 12			
Secondary				
• To assess the efficacy of namilumab 150 mg sc, given on Weeks 0, 2, 6 and 10 on other clinical responses in subjects with axSpA	 Proportion of subjects who achieve ASAS40 and ASAS70 response at Week 12 Proportion of subjects who achieve an ASAS20 clinical response at Week 6 Proportion of subjects who achieve ASDAS-CRP response at Weeks 6 and 12 			
• To assess the safety and tolerability of namilumab 150 mg sc, given on Weeks 0, 2, 6 and 10 in subjects with axial spondyloarthritis	 AEs SAEs Laboratory evaluations Vital signs Electrocardiograms (ECGs) Physical examinations Assessments of pulmonary function MRC breathlessness scale Chest x-ray Lung function tests Pulse oximetry Immunogenicity AEs of special interest: Pulmonary alveolar proteinosis (PAP) Neutropaenia Myeloid suppression 			

Objectives	Endpoints				
Exploratory					
 To assess the efficacy of namilumab 150 mg sc, given on Weeks 0, 2, 6 and 10 on radiologic responses in subjects with axial spondyloarthritis To assess the effect of namilumab 150 mg sc, given on Weeks 0, 2, 6 and 10 on other clinical responses, biomarkers, immunophenotyping, and pain scores in subjects with axial spondyloarthritis 	 Proportion of subjects who show a radiological response on MRI at 12 weeks Proportion of subjects who achieve ASAS20 clinical response at Weeks 2 and 10 Proportion of subjects who achieve ASDAS-CRP response at Weeks 2 and 10 Joint count, tendon swelling, and enthesitis at Weeks 2, 6, 10, and 12 Serum biomarkers including CRP, faecal biomarkers including calprotectin and microbiome Pre- and post-treatment immunophenotyping with CyTOF and gene expression (RNA seq) of CD4, CD8, CD56 and CD14 cells Neuropathic pain score (painDETECTTM) at Week 6 and 12 				

AE=adverse event; ASAS20/40/70=Assessment in Ankylosing Spondylitis with 20%/40%/70% improvement; ASDAS-CRP=Ankylosing Spondylitis Disease Activity Score C-reactive Protein; axSpA=axial spondyloarthritis; CyTOF=cytometry by time of flight; ECG=electrocardiogram; MRC=Medical Research Council; MRI=magnetic resonance imaging; PAP=pulmonary alveolar proteinosis; SAEs=serious adverse events.

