4.2.5 Justification for Primary Endpoints

The primary endpoint, Assessment in Ankylosing Spondylitis with 20% improvement (ASAS20) clinical response at 12 weeks, and the secondary endpoints, ASAS40, ASAS70, Ankylosing Spondylitis Disease Activity Score C-reactive Protein (ASDAS-CRP) response, and improvement of CRP, are consistent with the revised EMA Draft guidance (12 October 2017) for studies in axSpA.

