0.12 x back pain + 0.06 x duration of morning stiffness + 0.11 x patient global assessment + 0.07 x peripheral pain/swelling + 0.58 x ln (CRP + 1)

Values below the CRP threshold will be computed as half of the value of the threshold.

For disease activity states, the following defined cut-offs will be used: ASDAS <1.3 to define "inactive disease", $1.3 \le ASDAS <2.1$ to define "moderate disease activity", $2.1 \le ASDAS \le3.5$ to define "high disease activity", and ASDAS >3.5 to define "very high disease activity". A change of ≥ 1.1 units represents "clinically important improvement", and a change of ≥ 2.0 units represents major improvement.

Magnetic Resonance Imaging

An MRI of the axial skeleton will be taken at the times indicated in the SoA. The MRI will be obtained using 1.0, 1.5 or 3.0 Tesla scanners and phase array coils. Sagittal images of the upper (including C2 to T10) and lower (including T8 to S1) spine will be taken. The field of view is 34 to 38 cm. The following sequences may be used: T1 weighted turbo spin echo with a slice thickness of 3 mm and STIR (a sequence with intrinsic fat saturation) with a slice thickness of 3 mm.

MRI scans will be evaluated using Spondyloarthritis Research Consortium of Canada (SPARCC) MRI index for scoring inflammation of the spine.

Details of site training, MRI acquisition and central reading methods are detailed in the procedure manual for MRI examinations and the Imaging Review Charter (provided separately). MRI scans will be sent to the Central Imaging Laboratory. Specific shipping and transmitting instructions are provided in the procedure manual for MRI examination.

Immunophenotyping and Biomarker Evaluation

Pre- and post-treatment immunophenotyping with FACS, CyTOF and cell subset specific gene expression analysis (RNA seq and qPCR) of CD4, CD8, CD56 and CD14 cells will be performed. Blood, serum and urine will be analysed for protein and other biomarkers including genetic markers. Stool samples will be taken for microbiome analysis.

Neuropathic Pain Score

The painDETECTTM score (Freynhagen 2006) will be administered on Weeks 0, 6, 12 and 28. Absolute score and proportion fulfilling criteria for neuropathic pain on painDETECTTM score will be enumerated.

Joint Count, Tendon Swelling and Enthesitis

A swollen and tender joint count (68 joints) and the Leeds Enthesitis score (Healy 2008) will be performed on Weeks 0, 2, 6, 10 and 12.

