9.2 Sample Size Determination

The placebo prior = beta(p=0.3, n=20), and the prior for active is beta(p=0.6, n=5). The sample sizes are the smallest n such that the median Q(P{ $\theta_{act} > \theta_{pbo}$ | Y(H_A)}, 1 - γ) > Q(P{ $\theta_{act} > \theta_{pbo}$ | Y(H₀)}, γ), where Q(f, γ) represents the γ quantile from the distribution f, and Y(H_A) represents data generated under the alternative hypothesis, and Y(H₀) represents data generated under the null hypothesis. Sample sizes are shown in Table 9. The recommended sample size is 42 (6 on placebo, 36 on active). A plot of the distribution of P{ $\theta_{act} > \theta_{pbo}$ | Y} with both hypotheses overlapping as a function of the total sample size is shown in Figure 4.

Table 9 Sample Sizes for 6:1 Randomisation, Based on the Parameter y

γ	N Placebo	N Active	N Total
0.80	2	12	14
0.85	4	24	28
0.90	6	36	42

Figure 4Distribution of Posterior Probability $P(\theta_{act} > \theta_{pbo})$ as a Function of Total
Sample Size, Under Both Hypotheses

Shaded areas represent the middle 80% of the distribution (between the 10th and 90th percentiles).

9.3 **Populations for Analyses**

For purposes of analysis, the analysis sets in Table 10 are defined. For efficacy analyses, the Full Analysis Set (FAS) will be the primary analysis set, and the Per Protocol (PP) Analysis Set will be secondary. For safety analyses, the Safety Analysis Set will be the primary analysis set.

Analysis Set	Description		
Entered Analysis Set	All subjects who sign the ICF.		
Randomly Assigned to Study Treatment Analysis Set	All subjects in the Entered Analysis Set who are assigned to study treatment.		
Full Analysis Set	All subjects randomly assigned to study treatment and who take at least 1 dose of study treatment and have specific post-baseline assessments available.		
Per Protocol	All subjects in the Full Analysis Set that have week 10 efficacy data.		
Completer Analysis Set	All subjects in the Full Analysis Set who complete the study.		
Safety Analysis Set	All subjects randomly assigned to study treatment and who take at least 1 dose of study treatment. Subjects will be analysed according to the treatment they actually received.		

Table 10Analysis Sets

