9.4.1 Efficacy Analyses

Endpoint	Statistical Analysis Methods
Primary	The primary endpoint ASAS20 will be assessed using a Bayesian analysis. The control arm will have a beta prior with parameters rate = 0.3 and v = 20, and the namilumab arm will have a beta prior with rate 0.6 and v = 5. Posterior distributions will be calculated, and parameter distributions shown. The mean, standard deviation, and 5 th , 10 th , 25 th , 50 th , 75 th , 90 th , and 95 th percentiles of the posterior distribution will be presented. The posterior distribution will also be presented graphically. Given the observed data, the posterior probability $\eta \equiv P(\pi_{nam} > \pi_{pbo})$ will be calculated (Raineri 2014) and presented. Values of $\eta > 0.927$ will provide strong evidence that namilumab exhibits therapeutic benefit relative to placebo control. Missing data will be treated as non-responders for this analysis. For assessment of robustness of the analysis, the analysis will be performed on Completer Analysis Set.
Secondary	Summary statistics of ASAS20, ASAS40 and other efficacy endpoints will be summarised by visit
~ contain y	and treatment group. Summary statistics will be provided on both the Full and PP Analysis Sets.
Exploratory	Statistics used to summarise these endpoints will be described in the SAP.

Table 11Efficacy Analyses

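### MRI is scored on the numeric SPARCC spine index, but the SAP reports only a radiological response that neither document defines, with no summary of the score or its change

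*SAP*

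**What the plan says.** Protocol 8.1, under Magnetic Resonance Imaging, states: "MRI scans will be evaluated using Spondyloarthritis Research Consortium of Canada (SPARCC) MRI index for scoring inflammation of the spine". Scans go to a central imaging laboratory, and "central reading methods are detailed in the procedure manual for MRI examinations and the Imaging Review Charter", both provided separately.

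The one MRI endpoint, listed as exploratory in Protocol 3.0 (Table 4), is: "Proportion of subjects who show a radiological response on MRI at 12 weeks". For exploratory endpoints, Protocol 9.4.1 (Table 11) says: "Statistics used to summarise these endpoints will be described in the SAP".

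SAP 14.3.1.2 has a single sentence: "The radiological response is collected in an external data transfer and will be summarized descriptively in the Clinical Study Report". It gives no threshold, no summary of the score and no change from baseline. SAP 14.3.2 leaves missing exploratory data unimputed, apart from the ASAS and ASDAS-CRP responder endpoints. SAP 14.3.3 limits exploratory endpoints to description, with no testing.

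On the scans, footnotes 9 and 10 to the Schedule of Activities (Protocol 1.3) allow the pre-dose MRI to be up to 6 months before Screening. They make the Week 12 MRI optional and allow it to be done as late as Week 16.

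**The concern.** The protocol leaves the exploratory statistics to the SAP, and for MRI the SAP does not supply them. A reader with both documents cannot tell what change in SPARCC makes a responder. A reader of the planned table could not say how much spinal inflammation changed in either arm, or by how much the arms differ.

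This endpoint alone serves the objective on radiologic responses, and it is the only imaging measure of efficacy. The placebo arm has at most 6 subjects, so the placebo proportion can take at most 7 values (0/6 to 6/6), and fewer if optional scans are missed. In a group that small, collapsing a graded score to yes/no is costly. The central reading is planned anyway, so the score should exist whether or not it is tabulated.

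**Working it through.** **1. Is there a plan figure to reproduce?** No. The documents give no MRI response rate, SPARCC standard deviation, threshold, sample size or power. Everything numerical below rests on stated assumptions.

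**2. Planned summaries side by side (SAP 14.3.1).**

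| Measure | SAP section | Change from baseline planned? |
|---|---|---|
| Global assessment, spinal pain, BASFI, BASDAI | 14.3.1.1 | Yes |
| Swollen and tender joints, Leeds enthesitis | 14.3.1.5 | Yes |
| CRP, ESR | 14.3.1.6 | Yes |
| painDETECT | 14.3.1.8 | Yes |
| SPARCC spine score | 14.3.1.2 | No; response only |

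The ASAS responses and the ASDAS-CRP states have written cut-offs (SAP 14.1.1, 14.2.1). The radiological response has none in either document.

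**3. Information kept by a cut.** Assume a normal score with equal SD in both arms. Relative to the full score, a cut that makes a share p responders keeps φ(z_p)² / [p(1 − p)].

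| p | φ(z_p) | Kept | Lost |
|---|---|---|---|
| 0.50 | 0.399 | 64% | 36% |
| 0.40 | 0.386 | 62% | 38% |
| 0.30 | 0.348 | 58% | 42% |
| 0.25 | 0.318 | 54% | 46% |
| 0.20 | 0.280 | 49% | 51% |
| 0.10 | 0.175 | 34% | 66% |

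The function is symmetric about 0.5. The loss is therefore 36% to 46% for shares of 25% to 75%, and it exceeds one half only below about 21% or above about 79%.

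**4. At two different arm rates.** With no MRI rates available, borrow the ASAS20 planning rates (Protocol 1.1: "assuming true response rates of 0.3 and 0.6 for the control and namilumab arms, respectively"). Write v(p) = p(1 − p)/φ(z_p)², so v(0.60) = 1.608 and v(0.30) = 1.737. At 36 vs 6:

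- full-score variance: 1/36 + 1/6 = 0.194
- cut-based variance: 1.608/36 + 1.737/6 = 0.334
- ratio: 0.194/0.334 = 0.58

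About 42% of the information is lost. Equal precision from the cut would need about 1/0.58 = 1.7 times as many subjects.

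**5. Power, as a yardstick only (no test is planned).** The implied standardised difference is 0.253 + 0.524 = 0.78. At 36 vs 6, two-sided 5%:

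- Fisher's exact test on the cut: 19%
- t-test on the score: 41%
- baseline-adjusted: 44%, 51% and 67% at assumed correlations of 0.3, 0.5 and 0.7

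Fisher's test is conservative here, with a true size of about 2.3%. Run at that size, the t-test has 29% power. Of the 21-point gap, about 12 points (41 − 29) come from Fisher's discreteness and about 9 or 10 from the cut itself.

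**6. What the score analysis would deliver.** The unadjusted 95% half-width at 36 vs 6 is t(0.975; 40) × √(1/36 + 1/6) = 2.021 × 0.441 = 0.89 SD. That is the best case, because missed optional scans are not imputed.

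**The case against.** The case for leaving the plan alone has several sound parts.

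- **The definition may exist elsewhere.** The Imaging Review Charter may define response. A reader might infer that the endpoint is undefined altogether; the documents support only that the protocol and SAP do not state it.
- **The loss may be modest.** A reader might infer that most of the information goes. The working does not support that at mid-range response shares, and no MRI rate is given that would place the trial at an extreme one.
- **Power overstates the gap.** Much of the Fisher versus t-test difference is test conservatism, and SAP 14.3.3 rules out testing.
- **MRI is not the only objective readout.** SAP 14.3.1.6 summarises CRP and central-laboratory ESR, and joint counts are also summarised. Nor is MRI the only score reported just as a response: ASDAS-CRP is too, though with stated cut-offs.
- **Two further inferences fail.** One is that subjects with little spinal inflammation must count as non-responders, which depends on the unseen definition. The other is that the cited guideline bears on MRI: Protocol 4.2.5 calls the primary and secondary endpoints "consistent with the revised EMA Draft guidance (12 October 2017) for studies in axSpA", and its silence on an exploratory one shows nothing.
- **The scans are imperfect.** An early baseline scan and a late or missing Week 12 scan weaken change from baseline and the gain from adjustment.
- **Data are listed.** SAP section 14 lists all efficacy data, although it is unknown whether the SPARCC scores are in the transfer.

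All of this limits the size of the point. It does not supply a definition in the SAP or an arm-level summary of the score. Listings give individual values, not an estimate by arm.

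**Conclusion.** The point holds as an inexpensive improvement of low severity. A numeric score is to be read centrally, while the SAP plans only a response proportion, with no threshold stated in either document and no summary of score or change.

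Under a normal score with equal SD, the cut loses about 36% to 46% of the information at response shares of 25% to 75%, and about 42% at borrowed ASAS20 rates of 0.30 and 0.60. The true loss depends on the unknown MRI response rates and on the shape of the score. The power figures are illustrative, and 36 vs 6 is a ceiling.

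The endpoint is exploratory and the primary analysis is unaffected.

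**What to change.** Amend SAP 14.3.1.2 before unblinding:

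1. Obtain the baseline and Week 12 SPARCC spine scores in the same external transfer.
2. Summarise baseline, Week 12 and change by arm: number of paired scans, mean, SD, median and range. Report the timing of both scans.
3. Give a baseline-adjusted between-arm difference with a 95% confidence interval, by ANCOVA on the score or on log(score + 1), with a Hodges-Lehmann difference as a check. Label it exploratory, with no hypothesis test.
4. Add a line to SAP 14.3.3 permitting this estimate, since a modelled difference goes beyond pure description.
5. Keep the response proportion as a supplementary row and cite the charter's definition. If the charter has none, state and justify one in the SAP.

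The cost is SAP wording, one extra table and possibly two transfer fields; no further scans, reads, visits or subjects are needed. The score may be skewed or zero in some subjects, which the log and rank-based versions are there to handle. The estimate will still be imprecise and should be presented that way.

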14.3.1.6. Serum biomarkers including CRP, faecal biomarkers including calprotectin and microbiome

The change from baseline will be summarised descriptively for the following biomarkers: From eCRF: C-reactive protein (CRP) (quantitative variable) From central lab: Erythrocyte sedimentation rate

HLA-B27 will only be available at screening, therefore results will be listed only. Analysis of faecal calprotectin and microbiome analysis data will not be included in the clinical study report and will therefore be described in a separate analysis plan.

14.3.1.7. Pre- and post-treatment immunophenotyping with CyTOF and gene expression of CD4, CD8, CD56 and CD14 cells

Analysis of these parameters will not be included in the clinical study report and will therefore be described in a separate analysis plan.

14.3.1.8. Neuropathic pain score (painDETECT[™]) at Week 6 and 12

Change from baseline in painDETECTTM score derived in the eCRF will be summarized descriptively.

14.3.2. MISSING DATA METHODS FOR EXPLORATORY EFFICACY VARIABLE(S)

No imputation for missing data will be used for the exploratory endpoints with the exception of the endpoints related to ASAS and ASDAS-CRP responder that will follow the same rule used for the primary and secondary analysis (i.e. subject with missing data at the timepoint of interest will be considered as non-responder).

14.3.3. INFERENCE ON EXPLORATORY EFFICACY VARIABLES

The exploratory efficacy endpoints will only be analysed descriptively, and no hypothesis testing will be performed.

Document:	x:\biostatistics\documentation\sap\pya18238_izana_ izn-101	_sap_v1_0_2019050.docx	
Author:		Version Number:	1.0
		Version Date:	07May2019
Template No.:	CS_TP_BS016 Revision 5	Reference: CS_WI	_BS00

Effective Date: 01Apr2018

